After oral administration, TAM is oxidized by the cytochrome P450 enzymes, CYP3A4/5 and 2D6 to active metabolites (7, 8). These metabolites, together with the parent tamoxifen, function as competitive inhibitors of estrogen, binding to ER and thereby affecting ER's properties as a transcriptional regulator. The most active metabolites of tamoxifen are 4-hydroxytamoxifen and endoxifen (9, 10). They have a higher affinity for ER and are more potent than tamoxifen in suppressing estrogen-dependent cell proliferation (11-13). Genetic and environmental factors can affect the concentrations of active TAM metabolites.

CYP2D6 genetic polymorphisms:

The CYP2D6 gene encodes the rate-limiting enzyme that catalyzes the conversion of tamoxifen into its metabolites. A highly polymorphic gene, it has at least 63 different major alleles known to date (14). These variant alleles have been associated with increased activity (*CYP2D6*2xn*) or with little (*CYP2D6*10, *17, *41*) or no activity (*CYP2D6*4, *5*). Phenotypes arising from variations of these genotypes have been described as either poor (PM), intermediate (IM), extensive (EM), or ultrarapid (UM) metabolizers. Approximately 10% of the Caucasian population carries variant alleles that code for an impaired enzyme with the most common variant being *CYP2D6*4* having a significantly altered function (15). At an allele frequency of 15–21% in the Caucasians population, this variant causes a splicing defect that results in a non-functional protein. Individuals described as UM metabolizers carry gene duplications and multi-duplications of functional alleles, which lead to up to 30% higher CYP2D6 expression and enzyme activity, commonly observed in Ethiopians (16) but occurring at relatively low frequency in Caucasians and Asians (15).

CYP3A4/5 genetic polymorphisms:

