CYP3A4 is genetically polymorphic and is thought to explain about 60-90% of observed variation in drug metabolizing capacity of patients and over 30 SNPs have been published (17, 18). *CYP3A4*1B*, with allele frequency of 2-9% in Caucasians has been associated with worse presentation of prostate cancer (19), however reports on its function are mixed. One report suggests an increase in expression as measured by higher promoter activity (20); another associated *CYP3A4*1B* with a significantly decreased CYP3A activity (21). Another study reported no significant change (22). On the other hand CYP3A5 which is also polymorphic and has a very common defective variant *CYP3A5*3*, that has an allele frequency of about 90% in Caucasians (23). This variant *CYP3A5*3* creates an alternative splice site that results in a frame shift and truncation of the protein hence no activity (24, 25).

CYP2D6, CYP3A4/5 polymorphisms and tamoxifen treatment:

Genetic variability in CYP2D6 has been reported to affect patients treated with tamoxifen. Goetz et al (26) reported that *CYP2D6*4* was an independent predictor of a higher risk of relapse and a lower incidence of hot flashes in postmenopausal women. Further studies revealed that patients receiving selective serotonin reuptake inhibitors (SSRIs) that inhibit CYP2D6 activity, for their hot flashes were at an increased risk of breast cancer relapse (26). SSRI antidepressants are commonly prescribed to treat hot flashes in women who take tamoxifen and some such as paroxetine and fluoxetine, are known to inhibit cytochrome CYP2D6 (27). Other studies have associated breast cancer patients carrying the *CYP2D6*4* genotype or other genotypes (*5, *10, *41) of reduced or absent enzyme activity with less likelihood of benefiting from tamoxifen chemoprevention (28), or with significantly more recurrences, shorter

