Patient would undergo standard of care surgical excision at completion of four week course of tamoxifen. We do not anticipate the four week therapy with tamoxifen to modify the surgical planning including type of breast surgery, sentinel node biopsy or to affect the clinical outcome. After completion of surgical excision they would be recommended routine adjuvant therapy including adjuvant chemotherapy, radiation therapy and at least 5 years of endocrine therapy as dictated by the patient's final stage.

This protocol does not prohibit patients enrolling in any other future investigational studies after completion of surgical excisions.

Dose Modifications And Delays

There will be no dose modification of tamoxifen therapy. The toxicity profile of four weeks of tamoxifen is unknown. In the event of any Grade 2 or higher toxicity during the study attributed to tamoxifen, it will be discontinued and patient will be permanently taken off the study.

VII. NONPROTOCOL THERAPY

Patients should not receive any cancer therapy other than that specified in the protocol or while on Tamoxifen.

Sex Hormonal Therapy

Patients should not receive any sex hormonal therapy such as birth-control pills, hormone replacement therapy or infertility medications while on this protocol.

Radiation Therapy

Patients may not receive any radiation therapy until the completion of the protocol therapy.

Anti-Hormonal therapy

Patients may not receive any hormonal therapy including Aromatase inhibitors or Raloxifene while on the protocol therapy. Patients should be off of these medications for at least 30 days prior to enrollment. They may receive the appropriate adjuvant therapy after surgery.

Alternative therapy

Patient shall not receive any herbal/alternative therapies such as flaxseed or soy products or other medications such as black cohosh.

Non-cancer therapy

Patient may continue all the therapies intended for other than cancer. Patients shall discuss the safety of receiving the concurrent non-cancer medications with the study investigator. If patients are on SSRI's they are not eligible.

VIII. PHARMACEUTICAL INFORMATIONTamoxifen [NSC#180973]

Tamoxifen is supplied in tablet form, each containing 20 mg.

Clinical Safety and Adverse Effects

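### Only SSRIs are excluded on apparent drug-interaction grounds, and the genotype–metabolite model has no term for other prescribed CYP2D6 or CYP3A4/5 modifiers

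*Combined protocol and SAP*

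**What the plan says.** Section VII (Nonprotocol Therapy, Non-cancer therapy) opens with "Patient may continue all the therapies intended for other than cancer". It continues "Patients shall discuss the safety of receiving the concurrent non-cancer medications with the study investigator" and ends "If patients are on SSRI's they are not eligible". No reason is given for the SSRI line. The likely one is in the Background (Section III), which says of SSRIs that "some such as paroxetine and fluoxetine, are known to inhibit cytochrome CYP2D6".

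The Background names two enzyme systems: "TAM is oxidized by the cytochrome P450 enzymes, CYP3A4/5 and 2D6 to active metabolites". It adds that "Genetic and environmental factors can affect the concentrations of active TAM metabolites". Section V genotypes both systems.

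Other products are barred, but not on stated metabolic grounds. Section VII says "Patients should not receive any sex hormonal therapy such as birth-control pills, hormone replacement therapy or infertility medications while on this protocol" and "Patient shall not receive any herbal/alternative therapies such as flaxseed or soy products or other medications such as black cohosh", and hormonal therapy and raloxifene are also excluded.

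On data and analysis:
- Section IV takes a complete medication history at baseline.
- The PK/PD part of Section V lists ethnicity, current age, age at diagnosis and menopausal status as the data to be collected. Co-medication is not listed.
- Section VI explores the pharmacogenomic data with Y = a + bG + e, G coded 0, 1 or 2. Its clinical-factor adjustment is for the treatment-versus-control comparisons, and co-medication is not among its examples.

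**The concern.** The Background treats the link between genotype, metabolite level and outcome as an unmet need, and the trial sets out to measure it. The Background also reports mean endoxifen of 88.6, 64.2 and 21.9 nM for two, one and no functional CYP2D6 alleles. A woman with two functional alleles who takes a permitted inhibitor enters the model at G = 2. If her enzyme were fully blocked she would sit near 21.9 nM, about one quarter of the level her genotype predicts (88.6/21.9 = 4.0). Enough such women would flatten the genotype slope and add scatter. The medication history that could identify them is collected, but no analysis is planned to use it.

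**Working it through.** The plan states no power, SD or sample size for this analysis, so there is no figure to reproduce. What follows is an illustration.

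**Inputs from the documents.** Mean endoxifen is 21.9, 64.2 and 88.6 nM for G = 0, 1, 2 functional alleles. The CYP2D6*4 frequency is 15–21%. Total accrual is 50, taken as 25 on tamoxifen (1:1 is inferred from the block size of 4; the Background instead mentions 28–30 treated women). Two-sided alpha is 0.05.

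**Assumptions not in the documents.** Non-functional allele frequency q = 0.20 with Hardy-Weinberg proportions; log-normal endoxifen with CV 50%; a share f of women on a modifier; and the strength of inhibition.

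**Slope without users.** Genotype probabilities are 0.04, 0.32 and 0.64, so E(G) = 1.6 and Var(G) = 2 × 0.2 × 0.8 = 0.32.
- E(Y) = 0.04 × 21.9 + 0.32 × 64.2 + 0.64 × 88.6 = 78.12
- E(GY) = 0.32 × 64.2 + 2 × 0.64 × 88.6 = 133.95
- Slope = (133.95 − 1.6 × 78.12)/0.32 = 28.0 nM per allele

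**Full block (all users at 21.9 nM).** Users have zero slope, so the overall slope is 28.0 × (1 − f): 25.7 at 8% and 22.4 at 20%.

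**One-level shift (88.6 to 64.2, 64.2 to 21.9, 21.9 unchanged).** Among users E(Y) = 0.36 × 21.9 + 0.64 × 64.2 = 48.97 and E(GY) = 0.32 × 21.9 + 1.28 × 64.2 = 89.18. Their slope is (89.18 − 1.6 × 48.97)/0.32 = 33.8. At 20% users the overall slope is 0.8 × 28.0 + 0.2 × 33.8 = 29.2, so there is no attenuation.

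**Simulated power, n = 25** (at least 3,000 trials per cell; separate runs agree to about 0.02; mean simulated slopes fall slightly below the formula values):

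| Users | Full block, as planned | Full block, users excluded | One-level shift, as planned | One-level shift, users excluded |
|---|---|---|---|---|
| 0% | 0.47 | – | 0.49 | – |
| 8% | 0.38 | 0.43 | 0.50 | 0.43 |
| 12% | 0.33 | 0.42 | – | – |
| 20% | 0.26 | 0.36 | 0.53 | 0.38 |

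**Adding a yes/no modifier term.** Under full block at 20% users, power rises from 0.26 to 0.38, but the slope stays attenuated at 22.4, because an additive term removes the mean difference and still pools the two slopes. Excluding users returns the slope to about 27. Under the one-level shift at 20% users, power with and without the term is 0.54 and 0.55, equal within simulation error.

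**Sensitivity to the error model** (full block, normal errors, q = 0.18, n = 25, 0% against 20% users): SD 25 nM gives 74% against 37%, SD 35 gives 50% against 25%, and SD 45 gives 33% against 20%. With n = 30 and SD 35 it is 57% against 30%.

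**The case against.** The strongest case against runs as follows.

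- **The dilution rests on near-complete inhibition.** This stands. Under the one-level shift the slope does not shrink, and excluding users only costs power. The documents support neither strength of inhibition, nor any prevalence of modifier use once SSRI users are out.
- **The analysis is exploratory and weak anyway.** Also true: on these assumptions power is below 50% with no users at all, and at 8% (two women in 25) exclusion gains only about five points. This limits the importance of the point. It does not remove the case for a fix that needs no new data.
- **Low exposure is observed.** Tamoxifen and its metabolites are measured in plasma and tissue, so an inhibited woman's low level is seen. But the model would still attribute it to genotype or residual error.
- **The investigator discussion covers co-medication.** It is framed around safety, not metabolism, and feeds no analysis.

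A reader might infer from the opening sentence of the rule that every drug other than an SSRI may continue, so that all CYP3A4/5 modifiers are allowed. The documents do not support that: sex hormones, infertility drugs, raloxifene and herbal products are barred, and any modifier among them goes too. Nor is there a size for the CYP3A4/5 part. Nothing was calculated for it, and one pharmacokinetic study cited in the Background found no significant association of CYP3A5*3 with plasma tamoxifen or its metabolites.

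**Conclusion.** The point holds as a gap in the exploratory pharmacogenomic analysis. Prescribed CYP2D6 modifiers other than SSRIs, and prescribed CYP3A4/5 modifiers outside the barred groups, are unrestricted, and the planned model cannot separate their effect from genotype. Under full block the slope falls by about the share of users, and power falls from 47% to about 38% (8% users) or 26% (20% users). Under a one-allele-level shift there is little or no loss. The prevalence of use, the CV and the strength of inhibition are all assumptions.

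A reader might also infer that the randomised Aim 1 and Aim 2 comparisons are compromised. They are not biased by this, because co-medication is a baseline characteristic balanced by randomisation in expectation. Lower active-metabolite exposure could at most dilute a tamoxifen effect, and the analysis fix would not change that. This is an inexpensive improvement, not a fault that threatens the trial's main conclusions.

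**What to change.** In the PK/PD part of Section V, add co-medication to the listed clinical data, and define a yes/no variable for use of a CYP2D6 or CYP3A4/5 modifier. Derive it from the baseline medication history against one reference list named in the plan. In Section VI, add this variable as a covariate to the genotype–metabolite models and report a sensitivity analysis excluding users. Read the two together: under strong inhibition the covariate recovers power but leaves the slope attenuated, while exclusion recovers the slope.

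The cost is one derived variable from data already collected. The sensitivity analysis has a smaller sample and can lose power when inhibition is partial (0.53 to 0.38 at 20% users in the illustration). The baseline history may date from up to four weeks before consent, so drugs started later could be missed, and the report should say so.

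No patient's treatment changes. Whether to alter the entry rule is the sponsor's clinical decision. Separately, the SSRI line in Section VII does not appear in the exclusion list in Section III, and the two must be reconciled.

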- (c) Core biopsy should definitively demonstrate invasive carcinoma.
- (d) Invasive carcinoma should be ER α receptor positive
- (e) The tumor should be approximately at least 1 cm, to account for variability in imaging and imaging occult disease (physical exam, mammography, ultrasound). We recognize that from time to time because of this variation, there might

not be enough tissue available for analysis after surgical excision but this will allow the greatest opportunity to capture as many eligible patients as possible.

- (f) Patients in whom surgical excision of the tumor is part of standard of care management
- (g) ECOG score of 0 or 1
- (h) Negative serum or urine β -hCG pregnancy test at screening for patients of child-bearing potential (this is routinely done if the patient is premenopausal and having surgery)
- (i) Consent to participate in DBBR (RPCI only)

Exclusion Criteria:

- (a) Male patients are not eligible for this study
- (b) Female patients with inoperable tumors or women with stage 4 disease diagnosed on CT, PET, PET/CT or bone scan.
- (c) Patients with diagnosis by FNA cytology only
- (d) Pregnant or lactating women
- (e) Prior therapy for breast cancer, including irradiation, chemo- immuno- and/or hormonal therapy
- (f) Patients receiving any hormonal therapy, e.g. ovarian hormonal replacement therapy, infertility medications etc., are not eligible
- (g) Nonmalignant systemic disease (cardiovascular, renal, hepatic, etc.) that would preclude the patient from being subjected to surgical excision
- (h) Psychiatric or addictive disorders that would preclude obtaining informed consent
- (i) Patients known or suspected to have hypercoagulable syndrome or with history of venous or arterial thrombosis, stroke, TIA, or pulmonary embolism
- (j) Women with non-invasive disease or microinvasion are not eligible.
- (k) Women undergoing neoadjuvant chemotherapy are not eligible
- (l) women currently on tamoxifen and raloxifene for prevention are not eligible
- (m) Patients shall not receive any herbal/alternative therapies such as flaxseed or soy products or black cohosh.
- (n) Patients with a known mutation in p53 (Li Fraumeni Syndrome)

Unevaluable patients are defined as patients who do not have enough tissue for study or who come off early on tamoxifen, and will be replaced on study.

IV. TREATMENT PLAN AND RESEARCH METHODS:

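### The exclusion list omits two eligibility rules that stand only in Section VII (SSRI use and 30 days off hormonal agents), and the genotype model has no term for CYP2D6 inhibitors

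*Combined protocol and SAP*

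**What the plan says.** The protocol sets eligibility in two places.

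- **Eligibility Criteria, exclusion items (a) to (n).** Section IV refers back to this list as the study's criteria. No item mentions SSRIs and none gives a washout period. Three items concern hormonal exposure. Item (e) bars any earlier treatment of the breast cancer, hormonal treatment included, without a time limit. The other two look only at present use. Item (f) reads "Patients receiving any hormonal therapy, e.g. ovarian hormonal replacement therapy, infertility medications etc., are not eligible", and item (l) reads "women currently on tamoxifen and raloxifene for prevention are not eligible".
- **Section VII, Non-cancer therapy.** The paragraph opens with "Patient may continue all the therapies intended for other than cancer", asks patients to discuss concurrent medicines with the investigator, and ends with "If patients are on SSRI's they are not eligible".
- **Section VII, Anti-Hormonal therapy.** After ruling out hormonal therapy during protocol treatment, with aromatase inhibitors and raloxifene as the named examples, it adds: "Patients should be off of these medications for at least 30 days prior to enrollment".

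Section III (Background) explains why SSRIs matter: "some such as paroxetine and fluoxetine, are known to inhibit cytochrome CYP2D6". Section VI gives the pharmacogenomic model as Y = a + bG + e, where G is the genotype score 0, 1 or 2. Nothing in that model represents concurrent medication.

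**The concern.** Two centers enroll, and randomization follows the investigator's decision that the criteria are met. If the list named as the criteria is shorter than the rules elsewhere in the protocol, the centers can apply different entry rules without noticing. Appendix 2 (Study Deviations) removes inadvertently enrolled patients who have a significant deviation from the criteria. A mismatch found late could therefore cost randomized patients in a trial of 50.

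There is also an analysis issue. The genotype-metabolite model reads metabolizer status from genotype alone. A woman with two functional CYP2D6 alleles who takes an inhibiting drug is scored as a full metabolizer, although her endoxifen may be low. That flattens the slope the model is meant to estimate. Section VII lets other non-cancer drugs continue, so the issue is not confined to SSRIs.

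**Working it through.** **Step 1. The two texts side by side.**

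| Situation at screening | Exclusion list (a)-(n) | Section VII |
|---|---|---|
| Taking an SSRI | No item applies | Not eligible |
| Earlier hormonal therapy for breast cancer | Barred by (e), no time limit | 30 days off requested |
| Currently on hormonal therapy, or on preventive tamoxifen or raloxifene | Barred by (f) or (l) | Barred during protocol therapy |
| Stopped a hormonal agent not given for breast cancer less than 30 days ago | No item applies | 30 days off requested |
| Herbal or alternative therapy | Barred by (m): "Patients shall not receive any herbal/alternative therapies such as flaxseed or soy products or black cohosh" | Barred |

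Rows 1 and 4 are the gaps. Row 2 also differs, because the list sets no time limit and Section VII names 30 days. Row 5 shows that one Section VII rule was carried into the list. The documents do not say which text prevails.

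**Step 2. Would a later check catch these women?** Section IV requires a complete medication history, so the information is collected. The pre-dose blood sample meant to confirm zero tamoxifen (Section V, PK/PD studies) is drawn in the tamoxifen arm only (Section IV and Appendix 1). It therefore cannot reveal recent exposure in a control patient.

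**Step 3. The plan's own power figures.** With 25 per arm (assumed: 50 patients split equally) and a two-sided Fisher's exact test at 0.05, exact enumeration gives 80.5% power at 70.5% vs 29.5% (difference 0.41) and 78.2% at 70% vs 30%. The stated 80% for Aim 1 is reproduced. Neither that figure nor the Aim 2 effect size of 0.91 uses medication as an input, so reconciling the texts changes neither.

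**Step 4. What an uncoded inhibitor does to the genotype model.** Section III gives endoxifen of 21.9 nM with the CYP2D6*4 genotype, and 64.2 and 88.6 nM with one and two functional alleles. If inhibition were complete, a woman with two functional alleles would sit at 21.9 instead of 88.6 nM, lower by a factor of 88.6 / 21.9 = 4.0, with G unchanged.

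Simulation inputs:
- From the protocol: the three means above.
- Assumed: 25 treated women; 30% low- or no-function alleles; between-patient CV of 50% or 70%; a share f of women at the 21.9 nM mean whatever their genotype.
- Test: log endoxifen regressed on functional-allele count, two-sided at 0.05. The log-scale SD is sqrt(ln(1 + CV²)), which is sqrt(ln 1.25) = 0.47 at CV 50% and sqrt(ln 1.49) = 0.63 at CV 70%.

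| Share f inhibited | 0% | 5% | 10% | 15% |
|---|---|---|---|---|
| Power, CV 50% | 84% | 75% | 65% | 57% |
| Power, CV 70% | 68% | 59% | 51% | 45% |

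Repeat runs agree within about two points. The level depends heavily on the assumptions. With 18% low- or no-function alleles, power at f = 0 and CV 50% is about 59%. With 29 treated women (Section III proposes genotyping 28-30), the CV 50% row is about 88, 80, 70 and 62%.

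**The case against.** The strongest reply is that the protocol already bars SSRI users. A general permission followed in the same paragraph by a specific exception is ordinary drafting. A complete medication history is taken, patients are told to discuss other medicines with the investigator, the investigator determines eligibility before registration, and Appendix 2 allows no exceptions to the criteria. The registration form is not in the text available for review and may carry both rules. All of this stands. It means the protocol does not permit such enrollment; it leaves an operational gap for anyone who screens from the list alone.

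The washout half is small, and that also stands. Items (e), (f) and (l) leave only women who recently stopped a hormonal agent not given for breast cancer. The Section VII wording is open-ended, so the absence of tamoxifen from its examples carries little weight.

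Three stronger readings are tempting, and the documents do not support them:

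- **That sites will enroll barred women.** Only that they could is supported.
- **That the tamoxifen arm is contaminated and the primary comparison weakened.** Section III says parent tamoxifen also binds the receptor, so an inhibited woman is still exposed. No effect on Aim 1 or Aim 2 has been shown.
- **That the simulated losses measure the defect.** The documents give no rate of SSRI use or of screening error, and only some SSRIs are said to inhibit CYP2D6. Putting every user at 21.9 nM is therefore a worst case. Section VI describes the pharmacogenomic analysis as exploratory and claims no power for it.

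Finally, if the SSRI rule stands and is followed, coding SSRIs adds nothing. The variable then earns its place through the other inhibiting drugs that Section VII lets continue.

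**Conclusion.** The point holds as an internal inconsistency in the eligibility rules, with one related gap in an exploratory model. The list named as the criteria omits the SSRI rule and the 30-day rule, and nothing says which text prevails. The practical consequence is possible mis-registration and possible removal after randomization. Its frequency cannot be estimated from the documents.

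The model gap is real whichever rule is kept, because Y = a + bG + e cannot separate low endoxifen due to genotype from low endoxifen due to a drug. The power losses in the table (at most 84% to 57% at CV 50% and 68% to 45% at CV 70%, over shares up to 15%) rest on an assumed inhibitor share, allele frequency, CV and full inhibition. They are a worst-case illustration and do not bear on the stated Aim 1 or Aim 2 power. The correction is worth making because it is cheap; the primary comparison is not shown to be at risk.

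**What to change.** 1. Reconcile the exclusion list with Section VII so that one eligibility list, used at registration by both centers, carries the same rules on SSRIs and on prior hormonal agents, including any time window and the agents it covers. Which rule stands is for the investigators to decide. If the registration form already carries these rules, bring the protocol list into line with it.
2. Derive an indicator for use of CYP2D6-inhibiting drugs from the medication history already taken, with the drug list fixed before the metabolite data are seen. In the exploratory genotype-metabolite model, treat use as inhibited metabolizer status instead of relying on genotype alone.

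The cost is an edit to the eligibility text and checklist and one extra derived variable. No additional samples or patients are needed, and no stated power figure changes.
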